## 8.3 Safety Assessments

Details regarding specific safety procedures/assessments to be performed in this study are provided. The total amount of blood/tissue to be drawn/collected over the course of the study (from prestudy to poststudy visits), including approximate blood/tissue volumes drawn/collected by visit and by sample type per participant, can be found in the Laboratory or Study Procedures Manual.

Planned time points for all safety assessments are provided in the SoA.

# 8.3.1 Physical Examinations

A complete physical examination will be conducted by an investigator or medically qualified designee (consistent with local requirements) per institutional standard. Height and weight will also be measured and recorded.

A brief directed physical examination will be conducted by an investigator or medically qualified designee (consistent with local requirements) per institutional standard.

Investigators should pay special attention to clinical signs related to previous serious illnesses.

# 8.3.1.1 Full Physical Examination

The investigator or qualified designee will perform a complete physical examination during the screening period. Clinically significant abnormal findings should be recorded as medical

history. The time points for full physical exams are described in Section 1.3. After the first dose of study intervention, new clinically significant abnormal findings should be recorded as AEs.

Investigators should pay special attention to clinical signs related to previous serious illnesses.

# 8.3.1.2 Directed Physical Examination

For cycles that do not required a full physical examination as defined in Section 1.3, the investigator or qualified designee will perform a directed physical examination as clinically indicated before study intervention administration. New clinically significant abnormal findings should be recorded as AEs.

Investigators should pay special attention to clinical signs related to previous serious illnesses.

# 8.3.2 Vital Signs

The investigator or qualified designee will take vital signs at screening, before the administration of each dose of study intervention at study visits and during the follow-up period as specified in the SoA. Vital signs include temperature, heart rate, respiratory rate, and blood pressure. Height will be measured at Visit 1 only. Weight will be measured at Visit 1; Day 1 of Cycles 1, 2, and 3; and during follow-up as specified in the SoA.

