## 1.3 Schedule of Activities

- 1.3.1 Schedule of Activities for Part 1: Dose Escalation and Confirmation for Arm 1 (MK-1088 Monotherapy) and Arm 2 (MK-1088 in Combination With Pembrolizumab), and for Arm 1 Crossover to Arm 2
- 1.3.1.1 Part 1, Arms 1 and 2, and Arm 1 Crossover to Arm 2: Screening Through End-of-Treatment Phase

Table 1 Schedule of Activities: Screening through End-of-Treatment Phase for Part 1, Arm 1 and Arm 2, and Arm 1 Crossover to Arm 2

Study Phase	Screening Phase a	Treatment Phase (3-Week Cycles)											End of Treatment	Notes	
Treatment Cycle/Title:	Screening (Visit 1)		Cycle 1				Су	cle 2		Cycle 3			Cycles 4 to 35	/Discon- tinuation	Notes
Treatment Days per Cycle:	Up to 28 days before Day 1 Cycle 1	Day 1 b	Day 2°	Day 8	Day 15	Day 1	Day 2°	Day 8	Day 15	Day 1	Day 8	Day 15	Day 1	At time of treatment discontinuation	Treatment Phase: Procedures, assessments, and samples are collected predose unless otherwise specified .
Scheduling Window (Days)	-28 to -1	0	0	±3	±3	±3	±3	±3	±3	±3	±3	±3	±3	+3	
Administrative Procedures															
Informed Consent	X														Documented IC must be obtained before performing protocol-specific procedures.  Participants may elect to continue study treatment beyond disease progression and will require additional consent.
Informed Consent for Optional Future Biomedical Research	X														This is optional for the participant.
Inclusion/Exclusion Criteria	X														
Participant Identification Card	X	X													Update with the treatment number at the time of treatment allocation.
Demography and Medical History	X														

**C** Confidential

Study Phase	Screening Phase a	Treatment Phase (3-Week Cycles)											End of Treatment	Notes	
Treatment Cycle/Title:	Screening (Visit 1)		Сус	ele 1			Су	cle 2		(	Cycle 3 Cycles 4 to 35			/Discon- tinuation	Notes
Treatment Days per Cycle:	Up to 28 days before Day 1 Cycle 1	Day 1 b	Day 2°	Day 8	Day 15	Day 1	Day 2°	Day 8	Day 15	Day 1	Day 8	Day 15	Day 1	At time of treatment discontinuation	Treatment Phase: Procedures, assessments, and samples are collected predose unless otherwise specified .
Scheduling Window (Days)	-28 to -1	0	0	±3	±3	±3	±3	±3	±3	±3	±3	±3	±3	+3	
Prior/Concomitant Medication Review	X	X		X	X	X		X	X	X	X	X	X	X	
Treatment Allocation		X													Treatment allocation may occur up to 3 days before C1D1.

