Part 1 Arm 1 and Arm 2: MK-1088 Administration/Dispense		X				X				X			X		MK-1088: taken orally QD from D1 through D21 of each treatment cycle.
Part 1 Arm 2: Pembrolizumab Administration		X				X				X			X		Pembrolizumab: administered IV Q3W on D1 of each treatment cycle.
Anticancer Therapy Status														X	Any changes in new treatment will be collected.
Disease Status														X	
Clinical Procedures/Assessme	nts														
Full Physical Examination	X													X	
Directed Physical Examination		X		X	X	X				X			X		
Height	X														
Weight	X	X				X				X				X	
Vital Signs	X	X	X	X	X	X	X	X	X	X	X	X	X	X	Obtain heart rate, respiratory rate, blood pressure, temperature.
12-lead Electrocardiogram	X	X	X			X	X								C1D1 and C2D1: Obtain predose and 2 hrs postdose. C1D2 and C2D2: Obtain predose.

Study Phase	Screening Phase a	Treatment Phase (3-Week Cycles)											End of Treatment	Notes	
Treatment Cycle/Title:	Screening (Visit 1)		Сус	le 1			Су	cle 2		(	Cycle :	3	Cycles 4 to 35	/Discon- tinuation	Notes
Treatment Days per Cycle:	Up to 28 days before Day 1 Cycle 1	Day 1 b	Day 2°	Day 8	Day 15	Day 1	Day 2°	Day 8	Day 15	Day 1	Day 8	Day 15	Day 1	At time of treatment discontinuation	Treatment Phase: Procedures, assessments, and samples are collected predose unless otherwise specified .
Scheduling Window (Days)	-28 to -1	0	0	±3	±3	±3	±3	±3	±3	±3	±3	±3	±3	+3	
ECOG Performance Status	X	X	x									X	Obtain within 72 hrs before the first dose of study intervention on D1 of each cycle.		
AE Monitoring	X	+											→	X	
Tumor Imaging Response Assessment (PCWG-modified RECIST 1.1 for prostate cancer participants; RECIST 1.1 for all other participants)	X	4 -	4										X	Treatment phase schedule:  Obtain every 9 weeks (±7 days)  After 54 weeks, obtain every 12 weeks (±7 days)	
Prostate cancer participants only: Bone Scan	X	4						·				Х	Tc99 bone scintigraphy (nuclear medicine bone scan) is required at screening and on-study at all protocol-required tumor assessment visits and when clinically indicated.  Tumor assessments visits:  Obtain every 9 weeks (±7 days)  After 54 weeks, obtain every 12 weeks (±7 days)		

Study Phase	Screening Phase a		Treatment Phase (3-Week Cycles)									End of Treatment	Notes		
Treatment Cycle/Title:	Screening (Visit 1)		Cycle 1 Cycle 2 Cycle 3 Cycles 4 to 35								/Discon- tinuation	Notes			

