Plasma for MK-1088 PK assay		X	X			X	X			X			X	X	On the day(s) of sample collection, participants must not take study medication until the predose PK and biomarker (Section 8.8) sample collections are complete. Document the time of the last MK-1088 dose (ie, at home) taken before PK collection.  C1D1 and C2D1: Obtain predose and 1, 2, 4, and 8 hrs postdose.  C1D2 and C2D2: Obtain predose (24 hrs after D1 dosing for C1 and C2)  C3, C4 and every 4 cycles (ie, C4, C8, etc): Obtain predose
Blood for Serum Biomarker Analysis		X				X				X					Obtain predose
Blood for RNA Analyses		X				X				X					Obtain predose
Tumor Tissue Collection															
Archival or Newly Obtained Tumor Tissue Collection	X														See detailed tissue collection requirements in the Procedure/Lab Manual.  Participants in Arm 1 who cross over to Arm 2 do not need to provide an additional sample.

PROTOCOL/AMENDMENT NO.: 002-01

AE=adverse event; aPTT= activated partial thromboplastin time; β-hCG=beta-human chorionic gonadotropin; C=Cycle; CR=complete response; CT=computed tomography; D=Day; ECOG=Eastern Cooperative Oncology Group; HIV= human immunodeficiency virus; MRI=magnetic resonance imaging; PCWG=Prostate Cancer Working Group; PET= positron emission tomography; PK=pharmacokinetic; PSA=prostate-specific antigen; PT/INR=prothrombin time/international normalized ratio; PTT= partial thromboplastin time; Q3W=every 3 weeks; QD=once daily; RECIST=Response Evaluation Criteria In Solid Tumors; RNA=ribonucleic acid; SOP=standard operating procedure; TSH=thyroid-stimulating hormone; WOCBP=women of childbearing potential.

- a Arm 1 crossover to Arm 2: Screening assessments obtained during Arm 1 may be eligible for crossover screening for Arm 2 if the assessments were obtained within 28 days before Arm 2 treatment initiation.
- b Laboratory tests should be performed within 3 days before the first dose of study intervention. An exception is hepatitis and thyroid serologies, which may be performed within 28 days before the first dose. Please refer to Section 8.3.4.1 for details.
- c C1D2 and C2D2 evaluations must be obtained within 24 hours after study intervention administration for C1D1 and C2D1.

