#### 2.2.3.1 MK-1088 Clinical Studies

The FIH study for MK-1088 was PN001, a single ascending dose study in healthy volunteers to assess the safety, tolerability, and PK of MK-1088. This study completed enrollment and achieved LPLV on 01-JUN-2021. The FIH study in healthy volunteers afforded the advantage of rapid dose escalation into the therapeutic dose range in the subsequent Phase 1/Phase 2 study in oncology patients while also offering more comprehensive and reliable measurement of MK-1088 plasma exposures to thoroughly characterize the PK of MK-1088. Single doses of 1, 3, 10, 25, 50, 100, 150, and 224 mg of MK-1088 were evaluated in PN001. Doses up to 224 mg were generally well tolerated, with no major AEs and SAEs observed at the dose range of 1 to 224 mg. Increases in blood pressure of up to 14 mm Hg along with increases in heart rate of up to approximately 2 to 13 bpm were observed over the dose range of 10 to 224 mg. One participant at the highest dose of 224 mg had a greater systolic blood pressure/heart rate response than others (3× mean) and diastolic blood pressure increase similar to mean but did not report any associated symptoms.

Plasma exposures in PN001 were generally dose proportional at the 1 to 224 mg dose range, with observed median  $T_{max}$  of 2 hours and apparent terminal  $t_{1/2}$  between 6 to 11 hours. The minimum  $C_{trough}$  concentration target of 0.3  $\mu$ M corresponding to >99% TE for  $A_{2A}$  and >80% for  $A_{2B}$  was successfully achieved at a single dose of 150 mg while the aspirational trough target of 1  $\mu$ M corresponding to >99% for  $A_{2A}$  and >90% for  $A_{2B}$  was attained at both the 12- and 24-hour time points at a dose of 224 mg of MK-1088, enabling QD dosing of MK-1088 in Phase 1b. Furthermore, no food effect was observed at the 50 mg dose. Data from this FIH study were applied to inform the starting dose and dose levels for PN002 based on overall safety, tolerability profile, and PK of MK-1088 from PN001.

Please refer to the IB for further details.

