## 4.3.1 Starting Dose for This Study

## 4.3.1.1 Rationale for Starting and Maximum Dose of MK-1088

The planned starting dose of MK-1088 is 100 mg po QD. This starting dose was informed by the results of the FIH study MK-1088 PN001, which is a randomized, placebo controlled, double-blind, single ascending dose trial conducted in healthy males and females of non-child-bearing potential to determine the safety and tolerability of MK-1088 as well as to characterize the PK of MK-1088 that can achieve acceptable exposure and trough concentrations for the desired level of target engagement of the A2A and A2B receptors. The study was conducted with a tablet formulation (platform tablet of 40% drug load spray-dried intermediate in hydroxypropyl methylcellulose acetate succinate LF) in Belgium.

Data from this study was incorporated into a pharmacokinetic model to project the anticipated pharmacokinetic profile for daily dosing and projected tolerable starting dose that balances safety with potential benefits.

The 100 mg dose is approximately 2-fold lower than the highest dose tested in PN001. Based on in vitro profiling, high levels of  $A_{2A}$  inhibition (>99% TE) and  $A_{2B}$  inhibition (>90% TE) are expected at a trough concentration of approximately 1  $\mu$ M in the absence of adenosine. While this trough concentration was achieved by a single dose of 224 mg in PN001, changes in blood pressure/heart rate measurements in an individual subject, and a general trend for increased blood pressure and heart rate measurement over baseline values with increasing MK-1088 dose was noted. A starting dose of 100 mg was recommended as a conservative approach at which pharmacological activity for MK-1088 is expected to be observed (>90% TE for  $A_{2A}$  and >80% TE for  $A_{2B}$ ) and comprehensive evaluation of the safety profile upon

PRODUCT: MK-1088

PROTOCOL/AMENDMENT NO.: 002-01

repeat dosing in an oncology patient population will be enabled. A 100 mg single dose was well tolerated in healthy volunteers and this starting dose provides the ability to have appropriate monitoring of patients after repeat dosing, before steadily increasing the dose. Exposures have increased dose proportionately up to 224 mg single doses in MK-1088 PN001.

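### No blood pressure reading is scheduled after a dose, despite a dose-related rise in healthy volunteers and an existing 2-hour ECG and PK draw

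*Combined protocol and SAP*

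**What the plan says.** **Timing of vital signs.** Section 8.3.2 states that the investigator or designee "will take vital signs at screening, before the administration of each dose of study intervention at study visits", and during follow-up. In Table 1 (Section 1.3) the treatment-phase header sets collection as "predose unless otherwise specified". The note on the vital-signs row is "Obtain heart rate, respiratory rate, blood pressure, temperature", with no time.

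**Where a postdose time was wanted, Table 1 gives one.** The ECG note reads "C1D1 and C2D1: Obtain predose and 2 hrs postdose". The MK-1088 plasma PK note reads "C1D1 and C2D1: Obtain predose and 1, 2, 4, and 8 hrs postdose". On Day 2 of Cycles 1 and 2, Section 6.1 holds the dose until that day's procedures are done.

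**What PN001 showed.** For doses between 10 and 224 mg, Section 2.2.3.1 reports: "Increases in blood pressure of up to 14 mm Hg along with increases in heart rate of up to approximately 2 to 13 bpm". One participant at 224 mg had a systolic BP and heart-rate response three times the mean, without symptoms. Median Tmax was 2 hours and terminal half-life 6 to 11 hours. Section 4.3.1.1, explaining the 100 mg starting dose, adds that "a general trend for increased blood pressure and heart rate measurement over baseline values with increasing MK-1088 dose was noted".

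**Use of the data.** Section 9.6.2 summarizes vital signs as appropriate. Section 4.3.1.3 bases the choice of RP2D on the totality of the safety data.

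**The concern.** BP is a safety signal that the protocol itself raises, yet every scheduled treatment-visit reading comes when drug concentration is at its lowest. The first BP on drug is on Cycle 1 Day 2, up to 24 hours after the first dose. The 2-hour ECG can supply a heart rate near median Tmax, but nothing scheduled supplies BP then.

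Other safeguards do not reliably fill the gap. Section 10.3.2 makes clinically significant vital-sign changes adverse events, and Section 8 allows unscheduled evaluations. A rise without symptoms, such as the one in the marked PN001 responder, has to be measured before either applies.

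Three of the five planned dose levels (400, 600 and 800 mg) exceed the highest PN001 dose. If BP rises after dosing and falls back by the next morning, the by-dose summaries that inform the RP2D would not show it.

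**Working it through.** The plan states no figure on this point, so there is none to reproduce. The check has four steps.

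**1. Count of scheduled readings (Table 1).** Vital signs are marked on Cycle 1 Days 1, 2, 8 and 15, Cycle 2 Days 1, 2, 8 and 15, and Cycle 3 Days 1, 8 and 15.

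- Readings in Cycles 1 to 3: 4 + 4 + 3 = 11.
- Cycle 1 Day 1 precedes any drug. The other 10 are predose under the Table 1 default and Section 8.3.2.
- With the single Cycles 4 to 35 column there are 12 treatment columns, of which 0 name a postdose time.
- The end-of-treatment and 30-day readings are not tied to a dose.

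**2. Concentration about 24 hours after a dose, relative to peak.** Inputs from Section 2.2.3.1: Tmax 2 h, half-life 6 to 11 h.

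- *Mono-exponential decline from 2 h:* 2^(−(24−2)/t½). Half-life 6 h: 2^(−22/6) = 0.079. Half-life 11 h: 2^(−22/11) = 0.25.
- *One-compartment oral model,* with ka chosen so that Tmax = ln(ka/ke)/(ka−ke) = 2 h. Half-life 6 h: ka = 1.34/h, C24/Cmax = 0.086. Half-life 11 h: ka = 1.71/h, C24/Cmax = 0.260. The steady-state trough-to-peak ratios are 0.086 and 0.257.

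The range is therefore about 8% to 26% of peak.

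**3. What a predose cuff would show of a 14 mm Hg peak.** The time of peak BP effect is not given, nor when the 14 mm Hg was measured. Two bounding assumptions:

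- *Effect proportional to concentration:* 14 × 0.079 = 1.1 to 14 × 0.26 = 3.6 mm Hg. The missed part is 14 − 3.6 = 10.4 to 14 − 1.1 = 12.9 mm Hg.
- *Effect proportional to A2B receptor engagement:* Section 2.2.3.1 links a trough of 1 µM to more than 90% A2B engagement and says that this trough "was attained at both the 12- and 24-hour time points at a dose of 224 mg of MK-1088". Section 4.3.1.1 describes the engagement figure as in vitro, without adenosine. The predose reading would be at least 14 × 0.90 = 12.6 mm Hg, so the missed part is at most 14 − 12.6 = 1.4 mm Hg.

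These figures apply to PN001 doses and are not extrapolated to 800 mg.

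**4. Dose range.** 400/224 = 1.8, 600/224 = 2.7 and 800/224 = 3.6.

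**The case against.** **Nothing in the plan is contradicted or invalidated.** Section 8.3.2 and Table 1 agree, the primary endpoints are DLTs, AEs and discontinuations due to an AE, and no rule uses a 2-hour BP. That is true. The point concerns what the schedule can reveal.

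**The key premise is unverified.** A material loss requires BP to peak near Tmax and fade by 24 hours, and the documents do not show that it does. If the effect follows A2A engagement (above 99% at the same trough), the missed part is under 14 × 0.01 = 0.14 mm Hg. Higher doses could narrow the gap further if exposure keeps rising. This stands, and it is why the range in the working is so wide. The present schedule cannot tell these cases apart.

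**Some readings may be postdose in practice.** Days 8 and 15 have no PK or biomarker sample, and Section 6.1 has doses after Day 1 taken at home. Six of the 10 on-drug readings in Cycles 1 to 3 could therefore follow a dose. Against this, the Table 1 default, Section 8.3.2 and Section 8.1.8.1 (staff give the dose at on-site visits) all point to predose. Any postdose reading would be an untimed departure from the schedule.

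**Small uncontrolled cohorts cannot estimate the effect well.** Assuming an SD of change of 8 to 12 mm Hg, the 95% confidence half-width is about 20 to 30 mm Hg with 3 participants, 8 to 13 with 6 and 5 to 7 with 14. Without a control, the change also mixes in time of day, fasting and procedures. This is fair and limits the new summary to description, but an individual marked responder would still be visible.

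**Conclusion.** The concern holds. No BP is scheduled near the 2-hour median Tmax at any treatment visit, although PN001 showed a rise that trended with dose and participants are already present for an ECG and PK sample at that hour. Scheduled on-drug readings fall where concentration is about 8% to 26% of peak.

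The BP effect missed for a 14 mm Hg peak lies anywhere from under 1.4 to about 13 mm Hg, depending on whether it tracks receptor engagement or concentration. The documents do not settle which. The concentration range assumes the PN001 half-life and Tmax carry over to these participants.

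PN001 doses were generally well tolerated, so this is a weakness in the safety data behind the RP2D rather than a sign of harm. It should be corrected. Confidence is medium because the timing of the BP effect is unknown.

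**What to change.** In Table 1 and Section 8.3.2, add BP with heart rate at 2 hours postdose on Day 1 of Cycles 1 and 2, alongside the existing ECG and PK draw. In Section 9.6.2, add a descriptive summary of postdose-minus-predose change by dose level within each arm.

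The cost is two cuff readings per participant (2 × 80 = 160 for the planned Part 1 sample, somewhat more if crossover participants repeat the schedule), one schedule note with matching text, one line in the analysis section and a little data entry. No extra visit is needed, and no dose, DLT or treatment rule changes. If the BP effect peaks later than 2 hours, a single reading then can still understate it.

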## 8.3.3 Electrocardiograms

A standard 12-lead ECG will be performed using local standard procedures. The timing of ECGs is specified in the SoA. Clinically significant abnormal findings should be recorded as medical history. Additional ECGs may be performed as clinically necessary.

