# 8.4 Adverse Events, Serious Adverse Events, and Other Reportable Safety Events

The definitions of an AE or SAE, as well as the method of recording, evaluating, and assessing causality of AE and SAE and the procedures for completing and transmitting AE, SAE, and other reportable safety event reports can be found in Appendix 3.

Progression of the cancer under study is not considered an AE unless it results in hospitalization or death as described in Section 8.4.6 and Appendix 3.

Adverse events, SAEs, and other reportable safety events will be reported by the participant (or, when appropriate, by a caregiver, surrogate, or the participant's legally authorized representative).

The investigator and any designees are responsible for detecting, documenting, and reporting events that meet the definition of an AE or SAE as well as other reportable safety events. Investigators need to document if an SAE was associated with a medication error, misuse, or abuse. Investigators remain responsible for following up AEs, SAEs, and other reportable safety events for outcome according to Section 8.4.3.

The investigator, who is a qualified physician, will assess events that meet the definition of an AE or SAE as well as other reportable safety events with respect to seriousness, intensity/toxicity and causality.

Adverse events will not be collected for participants during the prescreening period (for determination of archival tissue status) as long as that participant has not undergone any protocol-specified procedure or intervention. If the participant requires a blood draw, fresh tumor biopsy, etc, the participant is first required to provide consent to the main study, and AEs will be captured according to guidelines for standard AE reporting.

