# **Events meeting the AE definition**

• Any abnormal laboratory test results (hematology, clinical chemistry, or urinalysis) or other safety assessments (eg, ECG, radiological scans, vital signs measurements), including those that worsen from baseline, considered clinically significant in the medical and scientific judgment of the investigator.

- Exacerbation of a chronic or intermittent preexisting condition including either an increase in frequency and/or intensity of the condition.
- New conditions detected or diagnosed after study intervention administration even though it may have been present before the start of the study.
- Signs, symptoms, or the clinical sequelae of a suspected drug-drug interaction.
- Signs, symptoms, or the clinical sequelae of a suspected overdose of either study intervention or a concomitant medication.
- For all reports of overdose (whether accidental or intentional) with an associated AE, the AE term should reflect the clinical symptoms or abnormal test result. An overdose without any associated clinical symptoms or abnormal laboratory results is reported using the terminology "accidental or intentional overdose without adverse effect."
- Any new cancer (that is not a condition of the study). Progression of the cancer under study is not a reportable event. Refer to Section 8.4.6 for additional details.

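### Section 8.3.3 sends clinically significant ECG abnormalities to medical history with no time limit, contradicting the AE definition in Appendix 3, although 5 of the 7 scheduled ECGs follow the first dose

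*Combined protocol and SAP*

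**What the plan says.** Section 8.3.3 contains a single recording instruction: "Clinically significant abnormal findings should be recorded as medical history". It defers timing to the schedule ("The timing of ECGs is specified in the SoA") and also allows unscheduled ECGs, which fall under the same instruction.

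In Table 1 (section 1.3.1.1) the row "12-lead Electrocardiogram" is marked at screening, Cycle 1 Days 1 and 2, and Cycle 2 Days 1 and 2. The note reads: "C1D1 and C2D1: Obtain predose and 2 hrs postdose. C1D2 and C2D2: Obtain predose". No ECG is scheduled after Cycle 2 Day 2, and none at end of treatment.

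Other sections treat comparable findings differently:

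- Full physical examination (8.3.1.1): screening findings go to medical history, but "After the first dose of study intervention, new clinically significant abnormal findings should be recorded as AEs".
- Directed physical examination (8.3.1.2): "New clinically significant abnormal findings should be recorded as AEs".
- Laboratory assessments (8.3.4): clinically relevant changes during the study go to the AE part of the CRF.
- Appendix 3 (10.3.2), on events that meet the AE definition: abnormal laboratory results or "other safety assessments (eg, ECG, radiological scans, vital signs measurements), including those that worsen from baseline, considered clinically significant" by the investigator.

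Section 8.4 points to Appendix 3 for "The definitions of an AE or SAE, as well as the method of recording, evaluating, and assessing causality of AE and SAE". Section 8.4.1 makes AE reporting mandatory from allocation until 30 days after study intervention stops.

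**The concern.** For any ECG after the first dose, 8.3.3 and Appendix 3 give opposite instructions for the same finding. The sentence in 8.3.3 resembles the screening sentence of 8.3.1.1 without the post-dose sentence that completes it there.

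The choice of form matters because DLTs, AEs and discontinuations due to an AE are the primary endpoints (section 3). AEs receive CTCAE grading and a causality assessment (10.3.5) and are counted by dose level (9.6.2). Medical history as described in 8.1.4 is a baseline record, so an on-treatment arrhythmia entered there would look like a condition that predated treatment.

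A cardiovascular effect is a reasonable thing to look for. In the healthy-volunteer study, heart rate rose by about 2 to 13 bpm and blood pressure by up to 14 mm Hg over 10 to 224 mg, with a median Tmax of 2 hours (2.2.3.1). The post-dose ECGs are taken at that time. The planned doses here reach 800 mg.

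**Working it through.** The documents state no ECG total, so there is no planned figure to reproduce. The check is a count from Table 1 and a comparison of the recording rules.

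**1. Scheduled ECGs**

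| Visit | ECGs | Before first dose | After first dose | After first dose and in Cycle 1 |
|---|---|---|---|---|
| Screening | 1 | 1 | 0 | 0 |
| C1D1 (predose, 2 h) | 2 | 1 | 1 | 1 |
| C1D2 (predose) | 1 | 0 | 1 | 1 |
| C2D1 (predose, 2 h) | 2 | 0 | 2 | 0 |
| C2D2 (predose) | 1 | 0 | 1 | 0 |
| Total | 7 | 2 | 5 | 2 |

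- After the first dose: 5/7 = 71%.
- After the first dose and inside the DLT window, which 6.6.2 sets as Cycle 1: 2/7 = 29% of all scheduled ECGs, or 2/5 = 40% of the post-dose ones.
- The C2D1 predose ECG could reveal an effect that arose in Cycle 1, but it is taken at the start of Cycle 2 and is not counted above. The other two Cycle 2 ECGs bear on the AE endpoint only.

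**2. Rules side by side, for a new clinically significant finding after the first dose**

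| Source | Where it is recorded |
|---|---|
| 8.3.3 | Medical history |
| 8.3.1.1 and 8.3.1.2 (examinations) | AE |
| 8.3.4 (laboratory) | AE |
| 10.3.2 (names ECG) | AE |

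Section 8.3.3 is the outlier, and I found no statement of which section takes precedence.

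**3. What one unrecognised event could do to a dose decision**

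This step is conditional. Assume one treatment-related nonhematologic event of Grade 3 or higher in Cycle 1 that is detected only by ECG, filed as medical history, and not otherwise recognised. In a cohort of three evaluable participants, Table 3 then gives:

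- true 1/3 (S, stay) is read as 0/3 (E, escalate);
- true 2/3 (D, de-escalate) is read as 1/3 (S, stay).

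The documents give no basis for the probability of that chain of events, so I attach none.

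**The case against.** The strongest reply is that binding text already sends these findings to AEs. Section 8.4 refers definition and recording to Appendix 3. Appendix 3 names ECGs and separately includes conditions first found after dosing. Section 8.4.1 is written as an obligation, while 8.3.3 is only a recommendation. Section 8.1.4 treats medical history as prior, active or screening-diagnosed conditions, so a new on-treatment finding does not fit there. All of this stands, and it rules out any claim that the AE route is missing. It does not remove the conflict, because 8.3.3 is the procedure-specific text that a site would consult for an ECG.

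A reader might go further and infer that a misfiled finding could not become a DLT. The documents do not support that. Section 6.6.2 defines a DLT by a toxicity that the investigator grades and judges related, not by the form on which it is entered. It also counts related toxicity that ends treatment in Cycle 1. Section 9.6.2 lists ECG measurements for clinical review in their own right, and 9.7 has data examined continuously for dose-finding. These are safeguards, but clinical review does not by itself add an event to the AE counts.

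A reader might also attach the 5-of-7 figure to the DLT endpoint. Only two of those five ECGs lie in the DLT window.

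Finally, the healthy-volunteer signal is indirect. The protocol reports heart-rate and blood-pressure increases from that study but no arrhythmia or QT finding.

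**Conclusion.** The point holds as an internal inconsistency. Section 8.3.3 is wrong as written for the five of seven scheduled ECGs that follow the first dose, and for any unscheduled on-treatment ECG. It conflicts with Appendix 3 and differs from 8.3.1.1, 8.3.1.2 and 8.3.4.

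The consequence is possible misfiling of a treatment-emergent ECG finding outside the AE data, with possible under-recognition as an AE. For the two ECGs inside Cycle 1, and perhaps the C2D1 predose ECG, under-recognition as a DLT is also possible. This rests on a site following 8.3.3 literally instead of Appendix 3 and 8.4.1. Actual loss of events cannot be inferred from the documents. No sample size, interval or analysis method is affected. The matter deserves correction because it touches how the primary endpoints are captured and costs almost nothing to put right.

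**What to change.** Amend the recording instruction in 8.3.3 so that it states three things:

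1. Clinically significant ECG abnormalities found at screening or baseline are entered as medical history.
2. Clinically significant abnormalities that are new or worse after the first dose are entered as AEs under Appendix 3 and, when they occur in Cycle 1, are assessed against the criteria already in 6.6.2.
3. Findings between allocation and first dose follow the reporting window in 8.4.1.

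The third item is needed because sending everything before the first dose to medical history would create a new conflict. AE reporting starts at allocation, which Table 1 allows up to 3 days before Cycle 1 Day 1, so the Day 1 predose ECG may already fall inside the AE window.

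The cost is a short text change in one section, with matching site guidance. It needs no new ECGs, visits or data items, and no change to the statistical methods.
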